11.7.5.2 Pregnancy

Subjects will be counseled to inform the investigator of any pregnancy that occurs during study treatment and within 90 days after the last dose of the study drug.

If a female subject or the female partner of a male subject becomes pregnant while participating in the study, study drug must be permanently discontinued immediately. For male subjects, study drug does not need to be permanently discontinued if the female partner's pregnancy resulted from donated sperm or sperm banked before study drug

exposure ([Section 11.7.5.1](#)). The investigator must notify the Medical Monitor and Vertex GPS within 24 hours of the site's knowledge of the subject's (or partner's) pregnancy using the Pregnancy Information Collection Form.

If the subject is confirmed to be on study drug, the subject or partner will be followed until the end of the pregnancy, and the infant will be followed for 1 year after the birth, provided informed consent is obtained. A separate ICF will be provided to explain these follow-up activities. Pregnancy itself does not constitute an AE.

11.7.6 Pulse Oximetry

Arterial oxygen saturation by pulse oximetry will be measured at visits noted in [Table 3-1](#) and [Table 3-2](#). This will be assessed following a 5-minute rest (seated or supine) and before study drug dosing. At visits when study drug is taken at the site, pulse oximetry will be collected before the morning dose. This is a noninvasive measure of oxygen delivery to the tissues and has been correlated with clinical status and lung function.

11.7.7 Liver Function Test Parameters

Liver Function Testing

Liver function testing (ALT, AST, GGT, ALP, direct bilirubin, and total bilirubin) must be performed as noted in [Table 3-2](#) for serum chemistry, while subjects are receiving study drug treatment and at the Safety Follow-up Visit.

These blood samples should be processed and shipped immediately per the Laboratory Manual.

Subjects with new treatment-emergent ALT or AST elevations of $>3 \times \text{ULN}$ and clinical symptoms must be followed closely, including repeat confirmatory testing performed by the central laboratory within 48 to 72 hours of the initial finding and subsequent close monitoring of ALT and AST levels, as clinically indicated. In addition, if ALT or AST is $>5 \times \text{ULN}$, repeat follow-up levels must be obtained within 7 ± 2 days.

If a subject cannot return to the site for liver function testing, a local laboratory may be used. Elevations in LFTs at the local laboratory must be reported immediately to the Medical Monitor, and the subject must have the tests repeated and sent to the central laboratory as soon as possible (ideally within 48 to 72 hours).

Study Drug Interruption

Study drug administration **must be interrupted** immediately (prior to confirmatory testing), and the Medical Monitor must be notified, if any of the following criteria is met and confirmed with repeat testing:

- ALT or AST $>8 \times \text{ULN}$
- ALT or AST $>5 \times \text{ULN}$ for more than 2 weeks
- ALT or AST $>3 \times \text{ULN}$, in association with total bilirubin $>2 \times \text{ULN}$ and/or clinical jaundice

A thorough investigation of potential causes should be conducted, and the subject should be followed closely for clinical progression.

If no convincing alternative etiology (e.g., acetaminophen use, viral hepatitis, or alcohol ingestion) for the elevated transaminases is identified, regardless of whether ALT or AST levels have improved, study drug treatment must be permanently discontinued if repeat testing within 48 to 72 hours confirms the initial elevation. Subjects in whom treatment is discontinued for elevated transaminases should have their transaminases monitored closely until levels normalize or return to baseline.

Resumption of Study Drug

If an alternative, reversible cause of transaminase elevation has been identified, study drug may be resumed once transaminases return to baseline or are $\leq 2 \times$ ULN, whichever is higher. Approval of the Medical Monitor is required before resumption of study drug. Upon resumption of study drug, transaminases should be assessed weekly for 4 weeks. If a protocol-defined transaminase elevation occurs within 4 weeks of rechallenge with the study drug (with confirmation of the initial elevation by repeat testing within 48 to 72 hours), then the study drug treatment must be permanently discontinued, regardless of the presumed etiology.

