10.2 Administration

Study drug tablets will be administered orally. Subjects will receive the same number of tablets each day to maintain the blind. Refer to [Table 10-1](#).

Table 10-1 Study Drug Administration – Treatment Period

Treatment	Time	Drug(s) and Dose(s) Administered Route of Administration
VX-661/ivacaftor	AM	VX-661 100-mg/IVA 150-mg fixed-dose tablet IVA matching placebo tablet oral
	PM	IVA 150-mg tablet oral
Ivacaftor	AM	VX-661/IVA matching placebo tablet IVA 150-mg tablet oral
	PM	IVA 150-mg tablet oral
Placebo	AM	VX-661/IVA matching placebo tablet IVA matching placebo tablet oral
	PM	IVA matching placebo tablet oral

AM: morning; IVA: ivacaftor; PM: evening.

Study drug should be administered within 30 minutes after starting a meal with fat-containing food, such as a "standard CF" high-fat, high-calorie meal or snack, according to the following guidelines:

1. Study drugs will be administered after the start and before the end of a meal throughout each of the 2 Treatment Periods. It is recommended that the duration of each meal associated with study drug intake (i.e., breakfast and dinner/snack, as applicable) should not exceed 30 minutes.
2. Study drug should be administered q12h (\pm 2 hours). For each subject, all doses (morning and evening) of study drugs will be taken at approximately the same time each day. For example, the morning dose could be taken at 08:00 every morning and the evening dose could be taken at 20:00 every evening throughout the study.
3. At the Day 1 Visit, all subjects will be observed for 6 hours after the morning dose of the study drug.
4. The date, amount taken, and time of study drug administration, including whether food was taken with each dose, will be recorded for 2 days before PK sample collection and on the days of PK sample collection.
5. On days of scheduled visits, the morning dose of study drug will be administered at the site after predose assessments have been completed. The meal or snack will be provided by the site for the morning dose of study drug.

6. If a subject's scheduled visit is to occur in the afternoon, the following guidelines must be used:
 - o If the dose in the clinic will be within 6 hours of the subject's scheduled morning dose, the subject should withhold their morning dose of study drug, and the morning dose will be administered in the clinic.

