10.5 Study Drug Interruption

If study drug dosing must be interrupted for more than 72 hours, the Medical Monitor must be notified. In these instances, study drug dosing may only resume after approval by the Medical Monitor. Specific instructions for interruption for elevated LFT levels and elevated QTc levels are provided in [Section 11.7.7](#) and [Section 11.7.4](#), respectively.

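### The liver stopping rule requires study drug to be interrupted before confirmatory testing, yet makes a confirmed repeat test part of the trigger

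*Protocol*

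**What the plan says.** Protocol Section 11.7.7, under its Study Drug Interruption subheading, says that dosing has to stop "immediately (prior to confirmatory testing), and the Medical Monitor must be notified, if any of the following criteria is met and confirmed with repeat testing". Three criteria follow:

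- ALT or AST above 8 × ULN
- ALT or AST above 5 × ULN lasting beyond 2 weeks
- ALT or AST above 3 × ULN together with total bilirubin above 2 × ULN and/or jaundice

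Confirmation then appears in a separate step. Where no convincing alternative cause is found, "study drug treatment must be permanently discontinued if repeat testing within 48 to 72 hours confirms the initial elevation". The rechallenge rule in the same section has the same structure: a new protocol-defined elevation within 4 weeks of restarting leads to permanent discontinuation, "with confirmation of the initial elevation by repeat testing within 48 to 72 hours".

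The section orders repeat testing in its opening part. Subjects with new ALT or AST elevations above 3 × ULN who also have "clinical symptoms must be followed closely, including repeat confirmatory testing performed by the central laboratory within 48 to 72 hours". A further sentence, with no symptom condition, asks for follow-up levels at 7 ± 2 days when ALT or AST exceeds 5 × ULN.

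The general interruption section (10.5) gives no liver rule of its own: "Specific instructions for interruption for elevated LFT levels and elevated QTc levels are provided in" Sections 11.7.7 and 11.7.4 respectively.

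**The concern.** An action that must come before the repeat test cannot depend on the result of that test. Read literally, the trigger has not been met until the repeat is back, so a site may continue dosing until then and say that it followed the protocol. Another site will act on the parenthesis and stop at once. Medical Monitor notification sits in the same sentence under the same condition, so the site that waits has not triggered that safeguard either.

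A smaller gap lies beside this. Permanent discontinuation depends on a repeat within 48 to 72 hours. For a central-laboratory result, the only sentence that orders a repeat at that interval is limited to subjects with clinical symptoms. An asymptomatic subject above 8 × ULN is explicitly ordered only the 7 ± 2 day follow-up, so the result that the discontinuation rule needs may not exist.

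What is at stake is the safety of subjects, who may be as young as 12, under a mandatory hepatic stopping rule. No bias between treatments is claimed.

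**Working it through.** The plan states no figure on this point, so the check is mainly a reading of the text. The arithmetic only sizes the consequence.

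**Step 1: the sentence itself.** Let A be a first result that meets a criterion, and B a repeat that confirms it. The sentence sets the time of interruption at A, before the repeat. It sets the condition for interruption as A and B. At the time of A, B is unknown, so the condition is undecided when the action is due.

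**Step 2: does other text decide it?**

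| Place | What it adds |
|---|---|
| Protocol 9.5 (removal of subjects) | Refers to 11.7.7 |
| Protocol 10.4 (dose modification) | Permits the investigator to interrupt; does not require it |
| Protocol 10.5 (interruption) | Refers to 11.7.7; requires Medical Monitor notification only for interruptions beyond 72 hours |
| Protocol 11.7.7, discontinuation | Uses confirmation to decide permanence |
| Protocol 11.7.7, resumption | Uses confirmation to decide permanence after rechallenge |
| SAP 8.4.2 and 10.5 | Summarise liver test thresholds; no conduct rule |

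None of these removes the conflict. The two uses of confirmation for permanence do suggest the intent: stop on the first result, then use the repeat to decide whether the stop is final.

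**Step 3: size.** Inputs:

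- Dosing interval, from Section 10.2: "Study drug should be administered q12h", with VX-661 in the morning tablet only (Table 10-1).
- Time to the repeat, from Section 11.7.7: "repeat confirmatory testing performed by the central laboratory within 48 to 72 hours of the initial finding".

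Extra dosing occasions = delay ÷ 12 h: 48 ÷ 12 = 4 and 72 ÷ 12 = 6. 
Extra VX-661 100 mg doses (combination arm) = delay ÷ 24 h: 48 ÷ 24 = 2 and 72 ÷ 24 = 3. 
Immediate interruption: 0 of each.

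**Step 4: when it can arise.** Table 3-2 schedules serum chemistry at Weeks 2, 4 and 8 and at Weeks 18, 20 and 24. No dose is given at Weeks 8 and 24. Among scheduled visits after dosing has begun in a period, the question therefore arises at Weeks 2, 4, 18 and 20. It can also arise at any unscheduled test.

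**The case against.** The strongest reply is that the text says if, not only if. Section 10.4 lets the investigator interrupt treatment at any time, so a site that stops on the first result breaches nothing. The parenthesis has no purpose except to say that the site should not wait, and the surrounding rules give confirmation a different job. On this view the sentence is clumsy but one safe course is always open, and the 4 to 6 occasions arise only if a site ignores the word immediately.

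Most of that is true. The safe course is permitted and the intent can be recovered. But a stopping rule has to require the safe course, and this one also gives cover to a site that waits.

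Other points stand in part:

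- The criterion above 5 × ULN for more than 2 weeks already involves repeated measurement, so the conflict bears mainly on the other two criteria.
- A subject with jaundice is arguably covered by the symptomatic repeat-test rule. The 7 ± 2 day follow-up does order a repeat for others, but not at the interval on which the discontinuation rule depends.
- With the VX-661 terminal half-life of about 116 hours (Section 8.2.2), and assuming simple exponential decline, stopping lowers its concentration by only 1 − 2^(−48/116) ≈ 25% at 48 hours and 1 − 2^(−72/116) ≈ 35% at 72 hours. The dose count therefore overstates the short-term contrast in VX-661 exposure. This does not carry over to ivacaftor, whose half-life is about 12 hours.

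**Conclusion.** The concern holds. The interruption sentence is wrong as written: its condition cannot be known when its action is due, and one of its two readings continues dosing above a stopping threshold. Waiting costs about 4 to 6 further dosing occasions, against none for immediate interruption. This assumes that the repeat result is acted on at 48 to 72 hours; laboratory turnaround is not given in the documents and is not counted. How often subjects will meet a criterion is also not given, so no expected number of affected subjects can be stated.

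The effect is confined to safety conduct, and mainly to the criterion above 8 × ULN and the criterion above 3 × ULN with raised bilirubin or jaundice. Sample size, type I error and the primary analysis are unaffected. Because this is a mandatory safety rule, the correction is required, not optional.

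**What to change.** Delete the last five words of the quoted interruption clause, so that drug is interrupted and the Medical Monitor notified on the first qualifying result. For the criterion above 5 × ULN for more than 2 weeks, that is the first result showing that the elevation has lasted beyond 2 weeks. Keep confirmation by repeat test for permanent discontinuation only, including after rechallenge.

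In the same edit, state that the 48 to 72 hour repeat applies to every interruption criterion regardless of symptoms, and that the 7 ± 2 day follow-up is additional to it. It would also help to say whether a local-laboratory value counts as the first result, since Sections 11.7.2 and 11.7.7 leave that open.

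The drafting cost is one deleted phrase, a sentence or two and a memo to sites. The discontinuation rule already relies on the 48 to 72 hour repeat, so making it explicit adds no new kind of procedure. Section 13.2.3 still applies: the change needs investigator and sponsor agreement and submission to the required regulatory authorities. If it is judged to affect subject safety significantly, it also needs IRB/IEC notification before implementation, unless it is needed to remove an immediate hazard.

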11.7.8 Ophthalmologic Examination

Subjects will undergo an ophthalmologic examination performed by a licensed ophthalmologist at Screening, which includes

- measurement of best corrected distance visual acuity of each eye
- measurement of lens refracting power following cycloplegia (e.g., autorefractor or ophthalmoscopy streak)
- pharmacologically dilated examination of the lens with a slit lamp

The screening ophthalmologic examination must be completed and the results reviewed before randomization. This examination does not have to be repeated if there is documentation of an examination that met protocol criteria and that was within 3 months before the start of the Screening Period. Subjects who have documentation of bilateral lens removal do not need the ophthalmologic examination.

If a cataract, lens opacity, Y-suture, or lamellar rings are identified and determined to be clinically significant by the ophthalmologist at the Screening examination, the subject is ineligible for study entry (see [Section 9.2](#)). If a cataract or lens opacity is identified and determined to be clinically significant by the ophthalmologist after dosing, the subject and Vertex Medical Monitor will be notified. After discussion with the Principal Investigator who collaborates with the Vertex Medical Monitor, the subject may elect to continue or discontinue study drug treatment. If the subject discontinues study drug treatment, the subject should complete the ETT and Safety Follow-up Visit (see [Section 8.1.6](#)). If the subject continues study drug treatment, more frequent ophthalmologic monitoring should be considered.

In addition to the screening examination, an ophthalmologic examination will be performed by a licensed ophthalmologist at the Safety Follow-up Visit or ETT Visit for the following subjects:

- subjects < 18 years of age at the Screening Visit who prematurely discontinue treatment after receiving at least 1 dose of study drug,
- subjects < 18 years of age at the Screening Visit who complete study drug treatment but do not enroll in a separate extension study of VX-661/ivacaftor within 28 days after the last dose of study drug.

This examination may be completed at either the ETT or Safety Follow-up Visit, but must be completed by the date of the Safety Follow-up Visit. Additional ophthalmologic examinations may be conducted at the discretion of the investigator. The Medical Monitor should be notified of any additional ophthalmologic examinations.

Subjects who have documentation of bilateral lens removal are not required to complete the eye examination at the Safety Follow-up Visit or ETT Visit.

In addition, at Screening, the following history will be obtained for all subjects:

- history of steroid use
- history or presence of diabetes
- any prior ophthalmologic or optometric examinations
- history of trauma to the eye
- any family history of glaucoma, congenital cataracts, or cataracts arising later in life
- use of corrective lenses (contact lenses or eyeglasses)
- history of prolonged exposure to sunlight or ultraviolet light and use of sunglasses
- history of exposure to secondhand smoke

12 STATISTICAL AND ANALYTICAL PLANS

This section presents a summary of the planned analyses for this protocol. Statistical analysis details will be provided in the Statistical Analysis Plan (SAP), and clinical pharmacologic analysis details will be provided in the Clinical Pharmacology Analysis Plan (CPAP), both of which will be finalized before the clinical data lock for the study and treatment unblinding.

12.1 Sample Size and Power

The primary efficacy endpoint is the absolute change in percent predicted FEV₁ from study baseline to the average of the Week 4 and Week 8 measurements in each Treatment Period.

The null hypotheses to be tested are that the mean change from study baseline in percent predicted FEV₁ to the average of the Week 4 and Week 8 measurements is the same for (i) VX-661/ivacaftor and placebo; and (ii) ivacaftor monotherapy and placebo.

Assuming a standard deviation (SD) of 7 percentage points, 30 subjects per sequence are needed to have at least 90% power to detect a 3 percentage point treatment difference between VX-661/ivacaftor and placebo when the mean values of the primary endpoint are being compared. A 2-sided significance level of 0.05 was used in the sample size calculations. Accounting for the hierarchical testing strategy, the proposed sample size will yield approximately an 85% chance of observing a statistically significant difference between ivacaftor monotherapy and placebo for the primary endpoint, under the assumption that ivacaftor monotherapy is also 3 percentage points better than placebo (refer to [Section 12.3.3.2](#) for a detailed description of the testing strategy). The sample size estimate was based on 10,000 simulation runs with an incomplete block design assuming no dropouts. In the simulation, the correlation between responses to the 2 treatments within a subject was assumed to be zero. After adjusting for an assumed dropout rate of 10%, the sample size was increased to 34 subjects per sequence (204 total subjects).

12.2 Analysis Sets

Assignment of subjects to analysis sets will be done before the clinical data lock for the study.

The All Subjects Set is defined as all subjects who were randomized or dosed (i.e., all subjects in the study). All subject data listings will be referenced using the All Subjects Set, unless otherwise specified.

The Full Analysis Set (FAS) is defined as all randomized subjects who carry the intended *CFTR* mutations (see [Section 16](#)) and who have received at least 1 dose of study drug. The FAS is to be used in efficacy analyses in which subjects will be analyzed according to the treatment to which they were assigned or according to the treatment sequence to which they were randomized. All analyses of background data and efficacy data will be based on the FAS.

The Safety Set is defined as all subjects who received at least 1 dose of study drug. The Safety Set is to be used for all safety analyses in which subjects will be analyzed according to the treatment they received. All analyses of safety data will be based on the Safety Set.

12.3 Statistical Analysis

The primary objective of this study is to evaluate the efficacy of VX-661/ivacaftor and ivacaftor monotherapy through 8 weeks of treatment in subjects with CF who are heterozygous for the *F508del* mutation on the *CFTR* gene and a second allele with a *CFTR* mutation predicted to have residual function.

This section presents a summary of the planned statistical analyses of efficacy and safety for this study. The Vertex Biometrics department or a designated CRO will analyze the data derived from this study. SAS[®] Version 9.2 or higher will be used to generate all statistical outputs (tables, figures, listings, and data sets).

Statistical analysis and presentation details will be provided in the SAP for the study.

12.3.1 General Considerations

All individual subject data for those randomized or exposed to study drug will be presented in data listings.

Continuous variables will be summarized using the following descriptive summary statistics: number of subjects (n), mean, SD, standard error (SE), median, minimum value (min), and maximum value (max). The precision of the measurement for each continuous variable will be specified in the SAP.

Categorical variables will be summarized using counts and percentages. Percentages will be presented to 1 decimal place.

Treatment emergent (TE) period for Treatment Period 1 will correspond to data from the first dose of study drug in the first period to the safety evaluation visit or 28 days after the last dose in the same period for subjects who do not have a safety evaluation visit. Similarly, TE period for Treatment Period 2 will correspond to data from first dose of study drug in the second period through the Safety Follow-up Visit or 28 days after the last dose in the same period for subjects who do not have an Safety Follow-up Visit.

Baseline: For this crossover study, 2 types of baseline will be defined. The **study baseline** is defined as the most recent nonmissing measurement (scheduled or unscheduled) collected prior to the first dose of study drug in the study. The definition will be applied to all demographics, background, and baseline characteristics and also efficacy data analysis, including the primary endpoint analysis. In addition, **period baseline** is defined as the most recent nonmissing measurement (scheduled or unscheduled) collected before the first dose of study drug in each Treatment Period. For Treatment Period 2, the baseline should be from an assessment measured after the TE period for Treatment Period 1. This definition will be applied to all safety data analysis. For ECG, baseline for Period 1 will be defined as the average of the 3 pretreatment measurements on Day 1. For sweat chloride, the study baseline value will be the mean of assessment values on the left and the right arm at the most recent time point before the first dose of study drug in the study.

Absolute change from study baseline will be calculated as post-baseline value – study baseline value.

Relative change from study baseline will be calculated as $100 \times (\text{post-baseline value} - \text{study baseline value}) / \text{study baseline value}$.

Absolute change from period baseline will be calculated as post-baseline value – period baseline value.

Relative change from period baseline will be calculated as $100 \times (\text{post-baseline value} - \text{period baseline value}) / \text{period baseline value}$.

